1. SYNOPSIS

Title: Randomized Double-Blind Study of Nitazoxanide Compared to Placebo in Subjects With HBeAg-Negative Chronic Hepatitis B Virologically Suppressed for at Least Twelve Months on Tenofovir Disoproxil Fumarate, Tenofovir Alafenamide or Entecavir

Study Number: RM08-2001

IND Number: 143,329

Indication: Treatment of hepatitis B e antigen (HBeAg) negative chronic hepatitis B (CHB).

Design: Randomized double-blind placebo-controlled dose-range-finding trial.

Number of Subjects: 48.

Population: Adults (at least 21 years of age) with HBeAg negative CHB virologically suppressed for at least 12 months on tenofovir disoproxil fumarate (TDF), tenofovir alafenamide (TAF) or entecavir (ETV).

Randomization: 1:1:1:1 (12 subjects per group).

Study Dose and Administration: Group 1: Placebo for 12 weeks.

Group 2: 600 mg nitazoxanide (NTZ) once daily for 12 weeks.

Group 3: 600 mg NTZ twice daily for 12 weeks.

Group 4: 900 mg NTZ twice daily for 12 weeks.

All subjects will continue TDF, TAF or ETV therapy throughout the study.

NTZ 300 mg extended release tablets and matching placebo tablets will be administered in double-blind fashion orally with food.

After 12 weeks, subjects will continue treatment with the same treatment regimen if they have achieved any decline in quantitative hepatitis B surface antigen (HBsAg) from Baseline to Week 12. Stopping rules are provided based upon mean change in quantitative (qHBsAg) response.

Objectives: To evaluate safety, effectiveness, and pharmacokinetic-pharmacodynamic (PK/PD) relationships associated with three different NTZ treatment regimens added to TDF, TAF or ETV in treating CHB.

Primary Efficacy Parameter: Mean change in HBsAg from Baseline to Week 12.

Secondary Efficacy Parameters:

- i. Sustained HBsAg loss with hepatitis B virus (HBV) deoxyribonucleic acid (DNA) suppression 24 weeks after end of treatment with NTZ and TDF, TAF or ETV.
- ii. Change in qHBsAg from Baseline to different time points on treatment.
- iii. HBsAg loss.
- iv. HBsAg seroconversion.
- v. HBV DNA suppression.
- vi. Change from Baseline in Fibrosis 4 (FIB-4) score.

vii. Change from Baseline in Fibroscan® score.

Safety Parameters: Adverse events, laboratory safety tests

Biological Samples: Blood and urine samples collected at Screening, Baseline (Day 1), Day 3, Weeks 1, 2, 4, 8, 12, 16, 20, 24 and every 12 weeks thereafter during treatment and at off-treatment follow-up Weeks 4, 8, 12, 24 and 48.

Study Center: National University Hospital of Singapore

Screening Period: August 2019 through April 2020

3. LIST OF ABBREVIATIONS AND DEFINITIONS OF TERMS

Table 1: Abbreviations

Abbreviation	Term
AFP	alpha-fetoprotein
ALT	alanine aminotransferase
AST	aspartate aminotransferase
BID	twice daily
BUN	blood urea nitrogen
cccDNA	covalently closed circular viral DNA
CHB	chronic hepatitis B
CPK	creatine phosphokinase
CRF	case report form
CTP	Child-Turcotte-Pugh
DNA	deoxyribonucleic acid
EDC	electronic data collection
ETV	entecavir
GCP	Good Clinical Practice
GGT	gamma glutamyl transferase
HBcAg	HBV core antigen
HBcrAg	HBV core-related antigen
HBeAg	Hepatitis B e antigen
HBsAg	Hepatitis B surface antigen
HBV	Hepatitis B virus
HCC	hepatocellular carcinoma
HCV	Hepatitis C Virus
HDV	Hepatitis D virus
HIV	human immunodeficiency virus
ICF	informed consent form
ICH	International Council for Harmonisation
IgM	Immunoglobulin M
INR	international normalized ratio
IRB	institutional review board
IUD	intrauterine device

Abbreviation	Term
NTZ	nitazoxanide
PT	prothrombin time
QD	once daily
qHBsAg	quantitative HBsAg
TAF	tenofovir alafenamide
TDF	tenofovir disoproxil fumarate

4. INTRODUCTION

4.1. Chronic Hepatitis B

Hepatitis B virus (HBV) is a partially double-stranded deoxyribonucleic acid (DNA) virus belonging to the Hepadnaviridae family of viruses.

Chronic hepatitis B (CHB) infection remains a major public health problem, affecting more than 250 million people worldwide. These patients have a higher risk of developing severe liver diseases such as cirrhosis, liver failure, or hepatocellular carcinoma ([World Health Organization, 2018](#)).

Currently available therapies for CHB include nucleoside/nucleotide reverse transcriptase inhibitors (NrtIs) and pegylated interferon. These therapies do not eliminate the covalently closed circular viral DNA (cccDNA), which functions as a nonreplicative minichromosome and persists throughout the lifespan of infected hepatocytes, and therefore, the goals of treatment are sustained suppression of HBV DNA and remission of liver disease. While six NrtIs have been approved by the U.S. FDA for treatment of CHB (tenofovir disoproxil fumarate (TDF), tenofovir alafenamide (TAF), entecavir (ETV), lamivudine, adefovir and telbivudine), TDF, TAF and ETV are the preferred NrtIs for treatment ([Lok et al, 2016; Terrault et al, 2018](#)).

Response rates for patients with hepatitis B e antigen (HBeAg) negative CHB enrolled in randomized clinical trials of TDF, TAF or ETV are as follows ([Terrault et al, 2018](#)):

HBV DNA suppression (less than 60 IU/mL) 90 to 93%.

alanine aminotransferase (ALT) normalization 76 to 88%.

Loss of hepatitis B surface antigen (HBsAg) less than 1%.

Long-term administration of NrtIs is standard of care for HBeAg-negative CHB because it reduces liver-related complications by suppressing viral replication. The best and safest stopping rule is HBV DNA suppression with loss of HBsAg. Loss of HBsAg is associated with reduced risk of hepatic decompensation and improved survival ([Terrault et al, 2016; Sarin et al, 2016; European Association for the Study of the Liver, 2017](#)). In this context, a treatment for CHB that could induce loss of HBsAg leading to functional cure is needed.

4.2. Nitazoxanide

Nitazoxanide (NTZ) is a thiazolidine anti-infective with *in vitro* activity against parasites, anaerobic bacteria, and viruses ([Anderson and Curran, 2007](#)).

Alinia® NTZ for Oral Suspension (patients 1 year of age and older) and Alinia NTZ Tablets (patients 12 years and older) are marketed in the United States for the treatment of diarrhea caused by *Giardia lamblia* or *Cryptosporidium parvum*. Alinia for Oral Suspension and Alinia Tablets have not been shown to be superior to placebo for the treatment of diarrhea caused by *Cryptosporidium parvum* in human immunodeficiency virus (HIV)-infected or immunodeficient patients ([Romark, 2017](#)).

4.2.1. Antiviral Activity of NTZ in Cell Cultures

Tizoxanide, the active metabolite of NTZ, has been shown to possess antiviral activity in cell culture against a broad range of viruses including influenza A and B viruses, parainfluenza

(Sendai) virus, respiratory syncytial virus (RSV) A-2, canine coronavirus S-378, rotavirus, norovirus, hepatitis C virus genotypes 1a and 1b, Japanese encephalitis virus, dengue fever virus-2, yellow fever virus, hepatitis B virus, and HIV. The wide spectrum of antiviral activity suggests a cell-mediated effect rather than a specific viral target (Rossignol, 2014).

In cell culture, tizoxanide suppresses HBV DNA in a dose-dependent manner ($EC_{50} = 0.15 \mu M$) and acts synergistically with lamivudine, adefovir dipivoxil, TDF and ETV. Unlike currently available therapies, tizoxanide also suppresses HBeAg and HBsAg in a dose-dependent manner at concentrations similar to those required to suppress HBV DNA (Korba et al., 2008; Romark data on file).

Recent studies have shown that NTZ inhibits HBV transcription from cccDNA by interfering with the interaction between HBV regulatory protein x (HBx) and the host protein, damage-specific-DNA-binding protein 1 (DDB1) (Sekiba et al., 2019).

4.2.2. Clinical Experience with NTZ

4.2.2.1. Overall Clinical Experience

NTZ has been marketed for diarrheal disease caused by *Giardia* or *Cryptosporidium* in the United States since 2003. In Latin America, India, Bangladesh and Egypt the drug is marketed as a broad-spectrum antiparasitic agent. It is estimated that more than 300 million patients have been exposed to NTZ worldwide with the usual adult dose being 500 mg twice daily for three days. No significant drug-related AEs have been reported in post-marketing experience.

Over 6,000 subjects have been treated with NTZ in clinical trials, including 1,760 subjects 12 years of age and older who have been exposed to the NTZ 300 mg extended release tablets (as monotherapy, $n = 1,272$, or in combination with oseltamivir, $n = 488$). Of the 1,760 subjects, 1,374 were given a dose of 600 mg twice daily for 5 days. The most commonly (at least 2% of treated subjects) reported adverse events (AEs) regardless of causality assessment were: diarrhea (6.4%), chromaturia (4.7%), headache (3.5%), nausea (3.1%), abdominal pain/abdominal pain upper (3%), bronchitis (2.7%), and vomiting (2.3%). In the placebo-controlled trials, the rates of occurrence of AEs did not differ significantly from those of placebo except for chromaturia (4.7% vs 0.2%). Less than 1% of subjects discontinued therapy because of AEs.

Other clinical studies of NTZ immediate-release tablets, oral suspension, or other formulations have been conducted in more than 4,250 subjects. The dose was typically 500 mg to 1500 mg twice daily for adults and adolescents at least 12 years of age or 7.5 mg/kg/day for children under 12 years of age, and the duration of treatment was typically 3 to 14 days.

The product has been studied for longer durations in subjects with acquired immune deficiency syndrome (AIDS) and cryptosporidiosis, and in subjects with chronic hepatitis C. A total of 660 subjects enrolled in these long-term studies received NTZ for more than 1 month (maximum of 1,528 days), of which 411 were treated for greater than 3 months, mostly at a dose range of 500 mg to 1350 mg twice daily. In 315 subjects with chronic hepatitis C, NTZ was administered at doses ranging from 500 mg to 1350 mg twice daily with food for up to 52 weeks. The AEs associated with long-term use of NTZ were primarily related to the gastrointestinal (GI) tract with mild to moderate and transient abdominal pain, diarrhea, headache and nausea being the most common AEs reported. Mild and transient yellow discoloration of the urine and sclera

have also been reported, particularly in subjects receiving doses of at least 1,000 mg BID for extended durations.

4.3. Rationale for the Study

There is a need for a new treatment of CHB that provides a functional cure with suppression of HBV DNA and loss of HBsAg. NTZ inhibits replication of HBV *in vitro* by means of a novel mechanism. It is unique in that it inhibits HBV transcription from cccDNA and suppresses HBV DNA while also suppressing HBeAg and HBsAg. This study will evaluate the effect of different doses of NTZ on quantitative HBsAg in an effort to identify a dosage regimen for further development with the objective of inducing loss of HBsAg.

5. STUDY OBJECTIVES

This randomized controlled trial is designed to evaluate safety, effectiveness and pharmacokinetic-pharmacodynamic (PK/PD) relationships associated with three different NTZ treatment regimens added to TDF, TAF or ETV in treating CHB.

6. STUDY DESIGN

The study will be a randomized, double-blind, placebo-controlled design. Forty-eight subjects will be selected according to the inclusion and exclusion criteria listed below. Upon enrollment in the study, subjects will be randomized to one of the following treatment groups (12 subjects per group):

- Group 1: PLACEBO

Subjects will take three placebo tablets twice daily.

- Group 2: 600 mg NTZ once daily (QD).

Subjects will take two NTZ 300 mg extended release tablets and one placebo tablet in the morning and three placebo tablets in the evening.

- Group 3: 600 mg NTZ twice daily (BID).

Subjects will take two NTZ 300 mg extended release tablets and one placebo tablet twice daily.

- Group 4: 900 mg NTZ BID.

Subjects will take three NTZ 300 mg extended release tablets twice daily.

NTZ and placebo tablets will be administered orally with food. All subjects will continue TDF, TAF or ETV therapy throughout the study.

After 12 weeks, subjects will continue treatment with the same treatment regimen if they have achieved any decline in quantitative HBsAg (qHBsAg) from Baseline to Week 12. The subjects will discontinue treatment with the investigational medication (NTZ and/or placebo) due to:

- Adverse events
- Withdrawn consent
- Noncompliance
- The subject fails to achieve any decline in qHBsAg from Baseline to Week 12, at least a 0.5 log₁₀ decline from Baseline to Week 24, at least a 1 log₁₀ decline from Baseline to Week 48, at least a 2 log₁₀ decline from Baseline to Week 72 or HBsAg loss at Week 96.
- The subject experiences HBsAg loss with HBV DNA suppression maintained on treatment for 24 weeks (consolidating therapy). TDF, TAF or ETV therapy will also be discontinued.

Subjects will return to the clinic at Day 3, Weeks 1, 2, 4, 8, 12, 16, 20, 24 and every 12 weeks thereafter during the treatment period. Blood samples will be collected at each visit for laboratory and/or serology tests. Blood samples for trough (just prior to dosing) plasma levels of NrtI and tizoxanide will be collected at Baseline and each scheduled visit while on therapy.

Subjects will return to the clinic for off-treatment follow-up at 4, 8 and 12 weeks following the end of treatment with investigational medication (NTZ and/or placebo). In the event that a subject has sustained HBsAg loss with HBV DNA suppression at the Week 12 follow-up visit, that subject will return for additional follow-up visits 24 and 48 weeks after the end of treatment.

The study will be unblinded to the Sponsor (Romark) and Medical Monitor after all subjects have completed 12 weeks of treatment and complete data is collected through that time point for

analysis of safety and the primary efficacy parameter (mean change in qHBsAg at Week 12). The investigators, subjects and clinical monitors will remain blinded throughout the study.

Rationale for study design: *In vitro* data suggest that NTZ may be effective in inducing loss of HBsAg in patients with CHB. Cell culture studies have shown that combinations of NTZ with the NrtIs, lamivudine, adefovir dipivoxil, TDF and ETV are synergistic in inhibiting HBV replication. The NrtIs are poorly effective in producing HBsAg loss or seroconversion, and therefore, patients must remain on chronic therapy in order to maintain suppression of HBV DNA. With this background, this study is designed to evaluate whether the combination of NTZ plus TDF, TAF or ETV is superior to TDF, TAF or ETV alone in reducing quantitative serum HBsAg. TDF, TAF or ETV were selected for use in this study because they are widely used for treating CHB and because of their potency in reducing serum HBV DNA and superior resistance profiles. This study is a Phase 2 study, and therefore, the number of subjects per treatment arm is low. This study is designed to provide data, including dose-range-finding data, to determine whether NTZ reduces qHBsAg and to guide future development of NTZ in treating CHB infection.

Rationale for dose and duration of treatment: The dose of TDF, TAF or ETV used in this study is the standard dose approved by the FDA and other regulatory authorities. The doses of NTZ were selected based upon safety, tolerability and pharmacokinetics data from prior clinical experience with nitazoxanide. Extended release tablets administered twice daily will be used to achieve steady state plasma concentrations of tizoxanide above the concentrations required to inhibit HBsAg in cell cultures. While it is expected that this approach will be optimal, a 600 mg once daily regimen will also be used to evaluate effectiveness. Two different doses (600 mg and 900 mg) will be used in twice daily regimens. These doses are lower than doses that have been used without safety issues in clinical trials involving long-term (at least 48 weeks) treatment of subjects with chronic hepatitis C or AIDS-related cryptosporidiosis. Doses of 1,000 to 1,350 mg NTZ twice daily have been associated with gastrointestinal side effects (e.g., epigastric pain, diarrhea) that make those regimens difficult to administer for long durations, and therefore, a maximum NTZ dose of 900 mg twice daily has been selected.

The duration of treatment to the primary endpoint (12 weeks) is designed to provide a relatively quick determination regarding whether NTZ induces a meaningful reduction of qHBsAg. Subjects will be allowed to continue treatment beyond 12 weeks if they are showing progressive declines in qHBsAg or if they experience HBsAg loss. The stopping rules require discontinuation of the investigational medication in the event that a subject fails to achieve any decline in qHBsAg from Baseline to Week 12, at least a 0.5 log₁₀ decline from Baseline to Week 24, at least a 1 log₁₀ decline from Baseline to Week 48, at least a 2 log₁₀ decline from Baseline to Week 72 or HBsAg loss at Week 96. The generally accepted stopping rule for peginterferon is less than a 1 log₁₀ decline of HBsAg at Week 12. The stopping rules for this study were selected because (1) there is insufficient information regarding the potential qHBsAg response patterns to NTZ and (2) use of NTZ for durations longer than 12 weeks has not been associated with significant safety issues. Subjects achieving HBsAg loss and HBV DNA suppression will continue treatment with the investigational medication and NrtI until they have maintained HBsAg loss and HBV DNA suppression for 24 weeks on treatment (consolidating therapy). The extended duration of treatment for subjects showing response to treatment is designed to allow subjects to continue treatment if they are experiencing benefit with respect to

qHBsAg. It also allows for collection of data regarding the duration of treatment for future clinical development.

7. SUBJECT SELECTION

The criteria for inclusion and exclusion are defined below:

7.1. Inclusion Criteria

1. Age at least 21 years.
2. CHB virus infection (serum HBsAg-positive for at least 6 months or serum HBsAg positive and negative immunoglobulin M (IgM) antibodies to HBV core antigen (IgM anti-HBc).
3. HBeAg negative.
4. Virologically suppressed (HBV DNA less than the lower limit of quantitation) for at least 12 months on TDF, TAF or ETV therapy.
5. Quantitative HBsAg greater than 100 IU/mL.
6. ALT below 1.5 times the upper limit of normal.
7. Able to comply with the study requirements.

7.2. Exclusion Criteria

1. Unable to take oral medications.
2. Females who are pregnant, breast-feeding or not using birth control. A double barrier method, oral birth control pills administered for at least 2 monthly cycles prior to study drug administration, an intrauterine device (IUD), or medroxyprogesterone acetate administered intramuscularly for a minimum of one month prior to study drug administration are acceptable methods of birth control for inclusion into the study. In addition, female subjects should have a Baseline pregnancy test and should agree to continue an acceptable method of birth control for the duration of the study (including follow-up) if sexually active.
3. Any investigational drug therapy within 30 days prior to enrollment.
4. Other causes of liver disease.
5. Co-infection with HIV, hepatitis C virus (HCV) or hepatitis D virus (HDV) based on an enzyme immunoassay (EIA).
6. History of alcoholism or with an alcohol consumption of greater than 40 g per day.
7. Clinically unstable.
8. Any concomitant condition that, in the opinion of the investigator would preclude evaluation of response or make it unlikely that the contemplated course of therapy and follow-up could be completed.

9. History of hypersensitivity or intolerance to NTZ or any of the excipients comprising the NTZ tablets.
10. Hepatocellular carcinoma.
11. Decompensated liver disease including history of ascites, bleeding esophageal varices, portal hypertension or hepatic encephalopathy.
12. FibroScan® score greater than 11 or history of cirrhosis on liver biopsy.
13. Creatinine clearance <65 ml/minute (by the Cockcroft-Gault equation using ideal body weight).
14. History of clinically relevant psychiatric disease, seizures, central nervous system dysfunction, severe pre-existing cardiac, renal, pathologic bone fracture or other risk factors for osteoporosis, hematological disease or medical illness that in the investigator's opinion might interfere with therapy.
15. Malignant disease within 3 years of trial entry.
16. Rheumatological conditions, inflammatory bowel disease or psoriasis requiring or anticipated to require biological/immunosuppressive therapies.
17. Subjects taking or anticipated to need medications considered to be major CYP2C8 substrates (see [Section 23.1](#)).

8. RANDOMIZATION

An independent third party will prepare a master randomization list and maintain the masking of the study. Subjects who qualify for the study will be assigned to treatment using centralized randomization procedures stratified by qHBsAg (less than 3, 3 to 4, greater than 4 \log_{10} IU/mL) and NrtI therapy (TDF, TAF or ETV). The treatment numbers will appear on the medication kits containing the masked study medication. The randomization list will be masked to study participants including Sponsor, Investigators, study monitors, subjects and laboratory personnel. Unmasking for any individual subject will occur only if necessitated by emergency and knowledge of the medication being taken will influence the medical management of the subject. Furthermore, if the event warrants submission of a safety report to regulatory authorities, then the subject's treatment assignment will be unmasked for completion of the report. If a subject is lost to follow up or discontinues the study prior to the assessment at week 12, an additional subject may be enrolled in the same treatment group.

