10. DATA MANAGEMENT

10.1. Electronic Data Entry

Data will be transcribed from source documents into an electronic data capture (EDC) system.

The responsible study monitor(s) will verify data, which can be performed remotely or at the clinical study site. The Investigator will ensure that the data recorded are accurate and complete.

Queries emerging during data cleaning will be generated within the EDC system by data management or clinical research associates. The Investigator or his/her designee will answer the queries and update the source data, if needed.

Adverse events and comorbid conditions will be coded by data management using the latest version of the Medical Dictionary for Regulatory Activities (MedDRA); medications will be coded by data management using the World Health Organization (WHO) DRUG dictionary.

After the Last Subject Last Visit (LSLV) has taken place, the database will be cleaned as necessary. As soon as the database is considered clean, it will be locked. The locked database will be used in the final statistical analysis for study reporting. Measures will be undertaken to protect subject data handled during inspections against disclosure to unauthorized third parties. Subject confidentiality will be maintained at all times.

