11.4. Statistical Methodology

The statistical methodology is described briefly below and will be described in detail in the Statistical Analysis Plan.

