11.4.1. Efficacy Analyses

The study will be unblinded to the Sponsor (Romark) and Medical Monitor for analysis of efficacy and safety data after all subjects have completed 12 weeks of treatment and complete data is collected through that time point. The investigators, subjects and monitors will remain blinded throughout the study.

Efficacy analyses will be based on a population consisting of all subjects randomly assigned to the study (“intent-to-treat” population). In the event that there are significant numbers of subjects who fail to complete the study, violate the protocol, or are noncompliant with the study medication, efficacy analyses will also be conducted for a population excluding these subjects (“per protocol population”).

Primary efficacy analyses will be conducted as follows: For each NTZ treatment group, the mean change in qHBsAg from Baseline to Week 12 will be compared to that of the placebo treatment group.

Secondary efficacy analyses will be conducted as follows:

- For each of the three NTZ groups, the proportion of subjects with sustained suppression of HBV DNA and HBsAg loss at 24 weeks after the end of treatment will be compared to the proportion for the placebo treatments group.
- For each NTZ dose group and for each study time point, the change in qHBsAg from Baseline will be compared to the change in qHBsAg for the placebo treatment group.
- For each of the three NTZ groups and for each study time point, the proportion of subjects with HBsAg loss will be compared to the proportion for the placebo treatments group.
- For each of the three NTZ groups and for each study time point, the proportion of subjects with HBsAg seroconversion will be compared to the proportion for the placebo treatments group.
- For each of the three NTZ groups and for each study time point, the proportion of subjects with quantifiable HBV DNA at Baseline who experienced HBV DNA suppression will be compared to the proportion for the placebo treatments group.
- For each NTZ dose group and for each study time point, the mean change in Fibrosis 4 (FIB-4) score from Baseline will be compared to the change for the placebo treatment group.
- For each NTZ dose group, the mean change in FibroScan® score from Baseline to end of treatment and to end of off-treatment follow-up will be compared to the change for the placebo treatment group.

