Change 15	Section 12.4, updated title to read: "Subject Compliance and Disallowed Medications" and added the following: "During the active treatment course of the study, concomitant use of medications considered major CYP2C8 substrates (Appendix I) are prohibited. Subjects are also prohibited from taking any other investigational medication during the study."
Change 16	Section 9.1 (Item #7), Section 9.2 (Item #8), Section 9.3 (Item #8), Section 9.4 (Item #6) and Section 9.5 (Item #6): Urine appearance was added to clinical laboratory testing.
Action:	A revised protocol version 3.0 dated June 13, 2019 was generated.
Amendment 3	
Purpose:	Revise protocol defined stopping rules, and other minor changes.
Change 1	Section 1, section 6, section 9.6 (item #4): Revised stopping rules.
Change 2	Section 1: Added study center and screening period.
Change 3	Section 2: Updated the study schema.
Change 4	Section 4.2.2.2: Changed "...treated with 500 mg nitazoxanide only once daily..." to "...treated with 500 mg NTZ only once daily...". Changed "...reviewed by Rossignol and Keeffe in 2009" to "...reviewed by Rossignol and Keeffe in 2008"
Change 5	Section 8: Added, "If a subject is lost to follow up or discontinues the study prior to the assessment at week 12, an additional subject may be enrolled in the same treatment group."
Change 6	Section 9.1 (Item #5): Changed HBV DNA to qHBV DNA and HBsAG to qHBsAg.
Change 7	Section 9.1 (Item #5), section 9.2 (Item #4): Changed anti-HBs to qAnti-HBs.
Change 8	Section 9.2 (Item #11): Removed "...for 12 weeks..." from the Group 3 and 4 dosing instructions and added "...with food..." to the Group 2 dosing instructions.
Change 9	Section 12.3: Added the following italicized language, "...every 4 to 12 weeks during the treatment period, depending on the visit schedule ."
Change 10	Section 21: Removed [REDACTED] as second Medical Monitor.
Change 11	Section 23.3: Added "(Table 5)" and removed "...on the following pages". Added "Table 5" and removed "...the next page".
Change 12	Amendment 2 Summary of Changes (Item #3): Changed "...Baseline and Week 1" to "...Baseline and visits throughout the study".
Action:	A revised protocol version 4.0 dated January 2, 2020 was generated.

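### Does the replacement rule in Section 8 leave the primary analysis set open to a choice made after unblinding?

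*Combined protocol and SAP*

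**What the plan says.** Protocol Section 8 (Randomization) assigns qualifying subjects centrally, stratified by qHBsAg level and NrtI. An independent third party holds the list, which is masked to the sponsor, investigators, monitors, subjects and laboratory staff. If someone is lost or discontinues before the Week 12 assessment, "an additional subject may be enrolled in the same treatment group".

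Section 11.4.1 (Efficacy Analyses) defines the main population: "Efficacy analyses will be based on a population consisting of all subjects randomly assigned to the study". A per-protocol set is added if many subjects fail to complete, violate the protocol or do not comply. Neither definition mentions additional subjects. The same section unblinds the sponsor and the "Medical Monitor for analysis of efficacy and safety data after all subjects have completed 12 weeks of treatment", once data to that point are complete.

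Section 11.1 plans 10 evaluable subjects per group and enrols 12 to allow for up to 2 non-evaluable. Section 11.4 says the methodology "will be described in detail in the Statistical Analysis Plan"; no separate SAP text is included in the documents available here.

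**The concern.** An additional subject enters an arm fixed by who left, so one could argue that this subject was not randomly assigned and falls outside the intent-to-treat set. One could equally argue the reverse, because Section 8 sends qualifying subjects through the central procedure. The text does not choose between the two in so many words. Nor does it say that the choice is made before the sponsor sees results by arm.

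Two other places seem to strengthen the worry. Section 10.1 places cleaning and lock after the last subject's last visit, well after the Week 12 analysis. The replacement sentence arrived with Amendment 3 ("A revised protocol version 4.0 dated January 2, 2020 was generated"), inside the screening window ("Screening Period: August 2019 through April 2020"), and that amendment lists no change to Section 11.

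With 12 subjects per arm, one or two subjects can move a p-value across 0.05. If the set were still open at unblinding, someone could choose the more favourable version.

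**Working it through.** **Inputs.** Section 11.1: difference 0.5 log10, SD 0.33, two-sided 5% t-test, 10 evaluable per group, up to 2 non-evaluable out of 12. Assumptions of this check: changes are normal, leavers go at random, and they have no Week 12 value and so drop out of the t-test.

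**The plan's own figure.** Noncentrality = 0.5 / (0.33 × √(1/10 + 1/10)) = 3.39 on 18 degrees of freedom, critical value 2.10. Power is 89.3%, against the stated 90%. The figure reproduces.

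**Power under each reading, two leavers per arm, both replaced.**
- Additional subjects not counted, 10 vs 10: 89.3%.
- Counted, 12 vs 12: noncentrality = 0.5 / (0.33 × √(1/12 + 1/12)) = 3.71 on 22 degrees of freedom, power 94.4%.
- Counted in one arm only, 12 vs 10: 92.0%.

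No reading falls below the planned power.

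**How far the two estimates can differ.** SD of the difference = 0.33 × √(2 × (1/(12 − k) − 1/12)) for k leavers per arm.
- k = 1: 0.041, so ±1.96 × 0.041 = ±0.080 log10.
- k = 2: 0.060, so ±0.118 log10, or 0.118 / 0.5 = 24% of the planning difference.

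The difference is centred on zero, so neither set favours an arm.

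**Type I error with no true effect** (simulation, 300,000 trials per setting).

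| Leavers replaced | Without additional subjects | With them | Better set picked afterwards |
|---|---|---|---|
| Two in each arm | 4.99% | 5.03% | 7.00% |
| One in each arm | 5.00% | 4.96% | 6.40% |
| One in one arm only | 5.02% | 4.98% | 5.99% |

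Either set holds 5%. The last column assumes someone always reports whichever set gives significance, so it is an upper bound.

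**Disagreement at the planned effect.** With two leavers per arm, the two sets give different verdicts in 6.6% of trials. Nearly all of this is the larger sample finding a real effect: about 5.9 points are significant only with the additional subjects, and about 0.8 only without (rounded separately).

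**The passages side by side.** Section 8 creates no class of non-randomised subjects, and Section 11.4.1 excludes nobody who was randomised. Read together, the leaver and the additional subject are both in the intent-to-treat set. Unblinding waits for all subjects to finish 12 weeks, so an additional subject already enrolled would be followed to Week 12 first. The lock in Section 10.1 serves the end of the study: "The locked database will be used in the final statistical analysis for study reporting". It says nothing about how the Week 12 data cut is controlled. Adding a replacement rule during screening while the sponsor is masked is not a defect either.

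**The case for a change.** The strongest case for acting is that certainty is cheap. One sentence would confirm that additional subjects count, and the sponsor would lose only the freedom to decide later. The study is meant to select a dose, so which comparisons reach p < 0.05 matters. Two leavers per arm is the protocol's own allowance, and masking before unblinding does not by itself fix a classification. At a true difference of 0.3 log10 the two sets disagree in 15.5% of trials.

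Some of this stands: the text never names additional subjects in an analysis set, and a confirming sentence would do no harm. The rest carries less weight. The 0.3 log10 difference is not a figure from the protocol. Power there is only 49% (10 vs 10) or 57% (12 vs 12), so verdicts are fragile under any rule, and 11.8 of the 15.5 points are again results significant only with the additional subjects. The error inflation requires someone to set aside the ordinary reading of the intent-to-treat definition after seeing results. The protocol also states that this early Phase 2 study makes no multiplicity adjustment. Three comparisons with one placebo group already give a family-wise error of about 12.6% by simulation at 12 per arm, so one or two points per comparison, only under deliberate picking, would hardly alter a development decision.

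**Conclusion.** The concern does not call for a change. The plan leaves a small gap in wording, and its own default fills it: everyone assigned through the central procedure is in the primary set, leavers and additional subjects alike. Followed that way, the analysis is sound. The 5% level holds, and power at the planned difference lies between 89.3% and 94.4% with up to two leavers per arm. The documents show no bias. The worst case, 7.0% per comparison, depends on post-hoc selection that nothing in the plan invites.

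These figures rest on the planned SD of 0.33, on leavers going at random, and on leavers having no Week 12 value. The protocol gives no rule for missing Week 12 values; if they were imputed, the figures would differ. If leaving were related to response, the missing values could bias the comparison under either set, and classifying the additional subjects would not cure that. The SAP to which the protocol defers may already state the classification.
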